6.4 ASSESSMENT OF INTENSITY

The investigator will assess the intensity for each AE and SAE reported during the study on the basis of his or her clinical judgement. The classifications in Table 4 should be used in assigning intensity of each AE recorded in the case report form.

Formatt

Dele

Table 4. Classification of AEs by Intensity^a

Intensity	Definition		
Mild AE (Grade 1)	An event that is easily tolerated by the subject, causing minimal discomfort and not interfering with everyday activities		
Moderate AE (Grade 2)	An event that is sufficiently discomforting to the extent of interfering with normal everyday activities		
Severe AE (Grade 3)	An event that prevents the subject from performing normal everyday activities		
Life-threatening or disabling AE (Grade 4)	An event that, at the time of occurrence, put the subject at risk of death or resulted in a persistent or significantly disability or incapacity		
Death related to AE (Grade 5)	An event that resulted in death		

AE = adverse event

Any AE that changes in intensity or grade during a single occurrence of an AE will be recorded in the eCRF at the highest level experienced by the subject.

An AE that is assessed as severe should not be confused with an SAE. Severity is a category used for rating the intensity of an AE (such as mild, moderate, or severe myocardial infarction). However, AE itself may be of relatively minor medical significance, such as a severe headache. Both AEs and SAEs can be assessed as severe. An AE is considered serious when it meets one of the predefined outcomes described in Section 6.1.

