1.1. STUDY OVERVIEW

Protocol HTD1801.PCT003 is a Phase 2, randomized, double-blind study which consists of a placebo- and dose-controlled parallel group period, a dose-controlled extension period, and a placebo-controlled randomized withdrawal period with the intent of comparing multiple doses of investigational product (HTD1801) to placebo. Approximately 60 patients with Primary Sclerosing Cholangitis (PSC) will be enrolled as subjects. Upon confirmation of eligibility, subjects will be randomized in Period 1 in a 1:1:1 ratio, stratified by inflammatory bowel disease (IBD) diagnosis and ursodiol (UDCA) status, to one of the following treatment arms:

- **Treatment Arm 1:** HTD1801 500 mg twice daily (BID)
- **Treatment Arm 2:** HTD1801 1000 mg BID
- **Treatment Arm 3:** Placebo BID.

Subjects will receive the treatment to which they are randomly assigned for 6 weeks during the first period.

In response to the COVID-19 pandemic, enrollment into the study was prematurely stopped on 25th March 2020. This impacted 3 subjects who had been randomized but had not yet initiated dosing. There may be additional restrictions associated with COVID-19 that may impact sites' ability to schedule subjects for in-clinic visits and thus, complete all protocol-required assessments. These will be noted as protocol deviations related to COVID-19 should they occur. These measures were put into place following the issuance of the FDA Guidance on Conduct of Clinical Trials of Medical Products during COVID-19 Pandemic (March 2020 and April 2020).

See [Section 3.2](#) for additional details on Period 1 randomization.

Following the completion of the first period, subjects are eligible to enroll in Period 2 which is a 6-week extension period. During this period, subjects who were previously randomized to 500 mg or 1000 mg BID in Period 1 will continue to receive the same dose. Subjects who were previously randomized to placebo will be randomized in a 1:1 ratio to receive 6 weeks of either 500 mg or 1000 mg BID. This period will continue to be double-blind.

Following the completion of Period 2, the 6-week treatment extension period, all subjects will be randomized in a 1:1 ratio to either continue on the active treatment they received in the second period or be assigned to placebo.

An independent Data and Safety Monitoring Board (DSMB) will provide additional safety oversight.

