3.3.7. Definitions and Terminology

Age

The age of a subject is defined as the number of whole years between the subject's birth date and the Period 1 treatment start date.

Day 1 (Baseline)

Day 1 is the earliest day that study drug is initiated in Period 1.

Study Day

Study Day is defined relative to Baseline (Day 1). Thus, the study day of an event is calculated as:

Study Day = event date – date of Day 1 (+ 1 if event date \geq date of Day 1).

Study Visit

Study Visit is the nominal visit as recorded on the CRF.

Weeks of Exposure

Weeks of exposure is calculated as the $(\text{Last Day on Study Drug} - \text{First Day on Study Drug} + 1) / 7$ within each period.

Treatment Compliance

Treatment compliance is calculated as the Number of Days of Dosing / Expected number of days of dosing within each period.

Baseline Value

For purposes of analysis, the baseline value is defined as the last non-missing value obtained prior to initiation of study drug.

Change from Baseline

Change from baseline for a given endpoint is defined as the Study Day X value minus the Baseline Value.

Adverse Event (AE)

An AE is defined as any untoward medical occurrence associated with the use of a drug in humans, whether or not considered drug related. An AE can be any unfavorable and unintended sign (including an abnormal laboratory finding), symptom, or disease (new or exacerbated) temporally associated with the use of the investigational product, regardless of whether it is considered to be related to the investigational product. All adverse events will be recorded on the Adverse Event CRF.

Treatment-emergent Adverse Event (TEAE)

A TEAE will be an AE that occurred during the study after the first dose of study drug or that was present prior to dosing and exacerbates after the first dose of study drug. Additionally, it is assumed that an Adverse Event which was reported to have started on Day 1 without an associated onset time occurred after the initiation of study drug.

Concomitant Medications

Concomitant medications are those medications taken on or after the initiation of study drug. This definition includes medications started prior to the initiation of study drug but continuing concomitantly with study drug.

Prior Medications

Prior medications are those medications taken prior to the initiation of study drug.

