5. STATISTICAL METHODS

Descriptive statistical methods will be used to summarize the data from this study, with hypothesis testing performed for the primary and other selected efficacy endpoints. Unless stated otherwise, the term “descriptive statistics” refers to number of subjects (n), mean, median, standard deviation (SD), minimum and maximum for continuous data and frequencies and percentages for categorical data. Additional statistical methods include mixed model repeated measures (MMRM), Student’s t-test (unpaired and paired), and Fisher Exact test. All data collected during the study will be included in data listings. Unless otherwise noted, the data will be sorted first by subject number, and then by Period and date within each subject number.

The term ‘treatment group’ refers to all subjects on the same dosing regimen. Efficacy and Safety tables will include only treatment groups that are present in the respective period being summarized. Safety tables will include all treatment groups. The treatment groups will apply for each period:

- Overall – Subjects will be summarized according to the period 1 treatment for demographic and screening information, or according to the actual treatment at the time of event or visit for safety summaries. AE summaries will use this format as well for the by period summaries.
 - Placebo
 - HTD1801 500 mg BID
 - HTD1801 500 mg BID
- Period 1 – Subjects will be summarized according to Period 1 treatment
 - Placebo
 - HTD1801 500 mg BID
 - HTD1801 500 mg BID
- Period 2 – Subjects will be summarized according to the Period 1 and Period 2 treatments
 - HTD1801 500 mg BID to HTD1801 500 mg BID
 - Placebo to HTD1801 500 mg BID
 - All HTD1801 500 mg BID (efficacy only)
 - HTD1801 1000 mg BID to HTD1801 1000 mg BID
 - Placebo to HTD1801 1000 mg BID
 - All HTD1801 1000 mg BID (efficacy only)

- Period 3 – Subjects will be summarized according to the Period 2 and Period 3 treatments
 - HTD1801 500 mg BID to HTD1801 500 mg BID
 - HTD1801 1000 mg BID to HTD1801 1000 mg BID
 - HTD1801 500 mg BID to Placebo
 - HTD1801 1000 mg BID to Placebo
 - All Active to Placebo

All statistical tests will be two-sided with an alpha level of 0.05.

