5.3. SAFETY

5.3.1. Adverse Events

AEs will be mapped to a Medical Dictionary for Regulatory Activities (MedDRA) version 20.1 preferred term (PT) and system organ classification (SOC). If a subject experiences multiple events that map to a single preferred term, the greatest severity grade according to the Common Terminology Criteria for Adverse Events (CTCAE) Version 4.0 will be assigned to the preferred term for the appropriate summaries. Should an event have a missing severity or relationship, it will be classified as having the highest severity and/or assumed related to study medication. The overall occurrence of any TEAEs, TEAE related to study drug, severe TEAEs, serious TEAEs, TEAE leading to discontinuation of study drug, and TEAE leading to death, alongside individual counts of each respective TEAE. The occurrence of TEAEs will be summarized by treatment group by SOC, and PT based on the treatment taken at AE start date. Summaries of the total number of subjects receiving each treatment and the average weeks of exposure for each treatment will be provided for context.

Separate summaries of each TEAE by period, TEAEs leading to the discontinuation of study, TEAEs related to study drug, and serious TEAEs will be generated and summarized by SOC and PT. The occurrence of TEAEs will be summarized by treatment group by SOC, PT, and Severity will also be summarized.

All adverse events reported will be listed for individual subjects showing verbatim term, PT and SOC. All AEs that occurred prior to the initiation of study treatment will be excluded from the tables but will be included in the listings.

Missing onset dates will be imputed as previously outlined in [Section 3.3.5](#) as required to determine treatment-emergent events.

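### An AE that worsens after the Week 6 or Week 12 re-randomisation is tabulated at its worse grade under the treatment the subject had before the switch

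*Protocol*

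**What the plan says.** Four rules bear on this.

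- **Recording.** Protocol 6.4: "Any AE that changes in intensity or grade during a single occurrence of an AE will be recorded in the eCRF at the highest level". The sentence does not ask for the date of the change. The Week 6, 12 and 18 visit instructions in Protocol 5.1 ask about changes to existing AEs, but give no instruction to close one record and open another.
- **Attribution.** SAP 5.3.1: "The occurrence of TEAEs will be summarized by treatment group by SOC, and PT based on the treatment taken at AE start date". SAP 5 gives the general basis for the overall and by-period AE summaries: "according to the actual treatment at the time of event or visit for safety summaries". The severity table is described separately, without restating the basis: "The occurrence of TEAEs will be summarized by treatment group by SOC, PT, and Severity will also be summarized".
- **Treatment emergence.** Besides AEs with onset after the first dose, SAP 3.3.7 counts an AE "that was present prior to dosing and exacerbates after the first dose of study drug". The anchor is the start of the study: "Day 1 is the earliest day that study drug is initiated in Period 1". For a subject randomised to placebo, that is the first placebo dose.
- **Several events under one preferred term.** SAP 5.3.1 assigns the greatest grade to the term and does not say that this is done within a treatment. Protocol 8.2.4 is similar.

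On the design, SAP 1.1 states: "Subjects who were previously randomized to placebo will be randomized in a 1:1 ratio to receive 6 weeks" of HTD1801 at one of the two doses. At Week 12 all subjects are randomised 1:1 to stay on their Period 2 treatment or go to placebo.

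**The concern.** Keeping the highest grade and attributing by onset are each reasonable in a parallel-group trial, where treatment is the same at onset and at the peak. Here treatment can change between the two. The event then carries a grade reached on one treatment into the column of another, and the treatment on which it worsened shows nothing.

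Safety and tolerability are secondary objectives. The Week 6 switch is the placebo subjects' first exposure to HTD1801, and the Week 12 switch is the withdrawal comparison, so worsening of an existing complaint is informative at both. The plan resets its reference point at the switches elsewhere: SAP 5.2.5 measures continuous endpoints from Week 6 in Period 2 and from Week 12 in Period 3, and SAP 5.3.2 builds Period 2 laboratory shifts from Week 6. AEs have no such reset.

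**Working it through.** The plan gives no figure to reproduce. The check applies the rules in order to two hypothetical AEs and then counts the switches.

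**Rule tracing**

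| Step | Week 6 switch | Week 12 switch |
|---|---|---|
| Onset | Grade 1, Week 5, on placebo | Grade 1, Week 11, on HTD1801 |
| Worsening | Grade 3, Week 8, on HTD1801 | Grade 3, Week 14, on placebo |
| Protocol 6.4 | one record, onset Week 5, Grade 3 | one record, onset Week 11, Grade 3 |
| SAP 3.3.7 | treatment-emergent once, from Day 1 | treatment-emergent once, from Day 1 |
| SAP 5.3.1 (treatment at onset) | placebo | HTD1801 |
| Tabulated as | Grade 3 on placebo, nothing on HTD1801 | Grade 3 on HTD1801, nothing on placebo |

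The start-date rule sends an ongoing AE that becomes serious, or leads to discontinuation, after the switch to the same column.

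**Switches, assuming everyone completes**

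Week 6: N/3 (the placebo third). Week 12: N/2.

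- N = 60 (SAP 1.1): 60/3 + 60/2 = 20 + 30 = 50.
- N = 90 (Protocol 8.2.7): 90/3 + 90/2 = 30 + 45 = 75.

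SAP 3.2 accounts for 42 + 17 = 59 randomised subjects, so N = 60 is the relevant case.

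**AEs spanning a switch**

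The documents give no AE rates. Assume that 10-30% of switches find one AE ongoing:

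- N = 60: 50 × 0.10 = 5 to 50 × 0.30 = 15, of which 2-6 are at Week 6 and 3-9 at Week 12.
- N = 90: 75 × 0.10 = 7.5 to 75 × 0.30 = 22.5.

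Only AEs that then worsen are misattributed. If f is the fraction that worsens, the number at N = 60 is f × (5 to 15). The documents do not inform f.

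**What a few such events do to a table (illustrative counts)**

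Suppose k = 1 to 3 of the 20 placebo subjects have an AE that becomes Grade 3 after the Week 6 switch.

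- As planned: 1/20 to 3/20 (5% to 15%) severe on placebo, and 0/20 on HTD1801 among these switchers.
- With worsening attributed to the treatment then taken: 0/20 on placebo, and 1/20 to 3/20 on HTD1801.
- With 30 placebo subjects: 1/30 to 3/30 (3.3% to 10.0%).

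In an overall column of everyone who ever takes placebo, the denominator at N = 60 is 20 + 40/2 = 40, and the same events are 1/40 to 3/40 (2.5% to 7.5%). The same k among the 30 subjects withdrawn at Week 12 shifts 1/30 to 3/30 (3.3% to 10.0%) the other way, from placebo to HTD1801.

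**The case against.** **Readings that go too far**

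- *The rule makes HTD1801 look safer.* A reader might infer this from the Week 6 switch alone. The Week 12 switches run the other way and are more numerous (30 against 20 at N = 60). Worsening need not be equally likely at the two, so the net direction is unknown.
- *The error cannot be repaired at analysis.* This would need knowledge of the eCRF, which is not among the documents. Protocol 6.4 does not request a date of change, but that does not show that none is captured. AEs are monitored at every scheduled contact, electronic entries are tracked (Protocol 8.1), and SAE reports are updated (Protocol 6.8). Some worsenings may be datable.
- *Five to 15 AEs are misattributed.* That range counts AEs ongoing at a switch, under an assumed rate. Those that worsen are a subset of unknown size.

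**Arguments that the plan already copes**

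- Protocol 6.1 lists exacerbation as an AE. It refers to preexisting conditions, whereas 6.4 is the specific rule for a grade change within one occurrence. If a site did open a second record, the greatest-grade rule in SAP 5.3.1 could still carry the worst grade across treatments.
- SAP 5.1 counts discontinuations by the treatment taken at the time. This stands for disposition. The SOC and PT table of TEAEs leading to discontinuation still follows onset, so the two outputs can disagree.
- Period 2 laboratory shift tables, subject listings and the DSMB give other views of safety. They do, but none corrects the AE tables.
- Severity is not a named endpoint in Protocol 3.3.2, and the start-date rule is not restated for the severity table. Both are true. Incidence by onset is counted correctly. Applying the rule to severity is an inference, but SAP 5 points the same way and no other basis is given.

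**Conclusion.** The point holds as a two-directional attribution error. Followed as written, the plan reports an AE that worsens after a switch at its worse grade under the earlier treatment: placebo at Week 6, HTD1801 at Week 12. The severity table, the serious TEAE table, and the SOC and PT table of TEAEs leading to discontinuation are affected. Incidence by onset, disposition and the primary ALP analysis are not.

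The size is an unknown fraction of the AEs ongoing at a switch. Those number about 5-15 at N = 60, given full completion and an assumed 10-30% of switches with one ongoing AE. The number is likely to be small, but in arms of about 20 a single event is 5%. The documents do not show which treatment is favoured overall, or that the dates are unrecoverable. The change is worth making before database lock.

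**What to change.** **Data.** When an AE ongoing at the Week 6 or Week 12 re-randomisation later worsens in grade or becomes serious, either open a new record dated at the worsening, or keep one record and add the date of worsening and the grade held at the switch. For AEs already recorded that span a switch, query sites for the same two items.

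**SAP 3.3.7 and 5.3.1.** Define an AE as treatment-emergent for a period if it starts, or worsens, on or after that period's first dose. Attribute it to that period's treatment, and say that this applies to the severity, serious and discontinuation tables. Take the greatest grade per preferred term within each treatment, not across the study. Without this last change, splitting records would not be enough.

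**Cost.** A few SAP sentences and some site queries. Opening new records departs from Protocol 6.4, and an amendment needs ethics approval under Protocol 9.4. Adding a date leaves the highest-grade record in place and is the lighter route, particularly as enrolment has already stopped (SAP 1.1). One clinical episode may give two records, so event counts rise slightly. No dose or clinical rule changes.

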6.5 ASSESSMENT OF CAUSALITY

The investigator must estimate the relationship between the investigational product and the occurrence of each AE or SAE by using his or her best clinical judgment. Elements to consider for this estimate include the history of the underlying disease, concomitant therapy, other risk factors, and the temporal relationship of the AE or SAE to the investigational product. The investigator will also consult the Investigator's Brochure or product label for marketed products in estimating the relationship.

Because of reporting timelines, the investigator might have minimal information to include in the initial SAE report. However, the investigator must always make an assessment of causality for every SAE before the transmission of the SAE report. The investigator may change his or her opinion of the causality in light of follow-up information, with subsequent amendment of the SAE report. Causality assessment is

a From Common Terminology Criteria for Adverse Events, version 4.0

one of the criteria used to determine regulatory reporting requirements and should not be left blank on the eCRF. The same applies to AEs that are to be processed as SAEs.

Table 5 provides some definitions to use in the assessment.

Table 5. Assessment of Causality of AEs

Term	Definition
Possibly related	The AE may be related to the investigational agent(s) or intervention: the AE has a temporal relationship to the administration of the investigational agent(s) or research intervention.
Unrelated (or not related)	The AE is clearly not related to the investigational agent(s) or intervention: the AE has no temporal relationship to the administration of the investigational agent(s) or research intervention, and follows no known or suspected pattern of response, and an alternative cause is present.

 \overline{AE} = adverse event.

6.6 EXPECTEDNESS OF SERIOUS ADVERSE EVENTS

An expected AE is one that is consistent with the known risk information described in the product label (if applicable) or the current Investigator's Brochure. The expectedness of an SAE will be assessed by the medical monitor and sponsor on receipt of the initial SAE report.

6.7 REPORTING OF SERIOUS ADVERSE EVENTS

- 1. Any SAE occurring after the subject signs the informed consent form and the investigational product has been administered, as described in Section 6.1, must be reported to the Medical Monitor by phone, fax, or e-mail within 24 hours of the time the investigator becomes aware of the SAE (Table 6). Any SAE reported by phone should be immediately followed up with the submission of the competed SAE report form. Urgent reporting of SAEs is required for the following reasons:
 - a. To enable the sponsor to fulfill the reporting requirements to the appropriate regulatory authority;
 - b. To facilitate discussion between the sponsor and the investigator about appropriate follow-up measures (if necessary);
 - c. To facilitate the sponsor's rapid dissemination of information about AEs to other investigators or sites in a multicenter study

d. To facilitate reporting unanticipated problems involving risk to subjects to the institutional review board (IRB) or independent ethics committee (IEC)

Table 6. Timeline for Reporting SAEs

Initial SAE Report		Follow-up SAE Report	
Time Frame	Documents	Time Frame	Documents
24 hours	SAE report	7 days	Updated SAE report

SAE = serious adverse event.

The SAE report will be completed as thoroughly as possible, including the following:

- Subject identification information
- Event term
- All available details about the SAE
- Causality of each SAE
- Signature of the investigator

The SAE report will be forwarded to the pharmacovigilance within the designated time frames. If additional information to complete the SAE report is needed, the investigator will not wait before notifying the safety department of the SAE. The SAE report will be updated by the investigator when additional information is received.

6.8 FOLLOW-UP OF ADVERSE EVENTS AND SERIOUS ADVERSE EVENTS

After the initial AE or SAE report, the investigator is required to proactively follow each subject and provide further information to the sponsor about the subject's condition. All AEs and SAEs will be followed until the occurrence of one of the following:

- The condition resolves.
- The AE or SAE is not related.
- The subject is lost to follow-up.
- The subject is followed for 30 days after the End-of-Study Visit (or other appropriate time frame).
- The subject starts another investigational product.

The appropriate SAE report will be updated once the SAE resolves, stabilizes, or is otherwise explained or until the subject is lost to follow-up. The investigator will also ensure that updates include any supplemental data that may explain causality of the SAE(s).

New or updated information will be recorded on a copy of the initial SAE report form; all incorrect data should be marked out (by a single line), initialed, and dated by the investigator or designee, with the new information clearly recorded. The updated SAE report form will then be signed and dated by the investigator and resubmitted to the pharmacovigilance department as outlined in Table 6.

